1. CLINICAL PROTOCOL

1.1. Background/ Rationale:

Neuropathic corneal pain, like neuropathic pain elsewhere in the body, is defined as pain resulting from a lesion/injury affecting the corneal somatosensory system on the ocular surface [1]. The increased numbers of patients with refractory corneal pain and discomfort following refractive surgery [2], and among patients with dry eye disease [3], has resulted in increased

Tufts Medical Center

interest by ophthalmologists and scientists to investigate the underlying mechanisms involved in NCP, and to search for new treatments to ameliorate neuropathic pain.

The cornea is highly innervated with sensory nerves, A δ - and C- fibers that originate from the ophthalmic branch of the trigeminal nerve. These nerves end in the corneal epithelium as free terminals [4]. These free nerve endings are classified as different types of nociceptors, depending on their responses to stimuli [5, 6].

Corneal pain signals are transmitted to the primary afferent fibers in the trigeminal ganglion (TG). From there second-orders neurons join the contralateral spinothalamic tract to synapse with third-order neurons in the thalamus. These ascending signals are further modified by input from subcortical structures associated with emotions and memory before terminating in the somatosensory cortex where they are felt as pain [7].

Injury to corneal nerves, associated with inflammatory responses may result in peripheral sensitization, which involves a decrease in nociceptor threshold for excitation, resulting in pain responses to typically non-painful stimuli (hyperalgesia) or even in the absence of stimuli (allodynia). Persistent nerve injury leading to prolonged and continuous signaling through the afferent fibers may subsequently lead to central sensitization, in which nociceptors outside the site of the original lesion undergo a similar process and can be activated by sub-threshold stimuli or even spontaneously discharge independent of any peripheral signaling [8, 9].

Peripheral neuromodulation involves applying electrical currents to peripheral nerves for medical therapy. Its evolution and expansion has increased over the course of the last two decades for the management chronic pain [7, 10]. The “gate control theory” provides the understanding for this concept, by which activation of large myelinated nerve fibers inhibits transmission of pain impulses from the peripheral nervous system to the central nervous system. The antegrade stimulation of nociceptive A δ nerve fibers leads to activation of interneurons in the TG. The same interneurons in the TG are also involved in the process of transmission of nociceptive signals from peripheral nerves. Non-painful stimuli from peripheral nerves, such as those conducted with the ITN, result in decreased excitability, increased electrical thresholds, transient slowing of conduction velocity, and result in inhibition of interneurons that leads to interruption of pain signal transmission from the territory innervated by the stimulated nerve [11, 12].

The TrueTear® ITN, recently approved by the FDA, is a portable neuromodulation device that delivers a small electrical current to the sensory nerves in the nasal cavity that stimulates the nasolacrimal reflex (NLR) [13]. The NLR afferent pathway emerges from the ethmoidal nerve, a subunit of the ophthalmic branch of the trigeminal nerve and ends at the interneurons in the TG.

2.0 STUDY OBJECTIVES

Hypothesis / Study Objective/ Purpose:

In our recent study using the TrueTear™ intranasal neurostimulator (ITN) in patients with dry eye disease (Dieckmann et al. ARVO 2017, unpublished observation) and concurrent neuropathic symptoms, some patients that suffered from neuropathic pain or photoallodynia, reported immediate relief of pain or photoallodynia after a single 3-minute use of ITN.

Thus, we hypothesize that the stimulation through the ethmoidal nerve in the nasal cavity may have an inhibitory effect on the primary TG interneurons and block the ocular pain signaling to the brain.

We propose a non-randomized, cross sectional, open-label, single arm pilot trial for treatment of neuropathic corneal pain (NCP) with ITN with the following specific aims:

Specific Aims:

1. To elucidate the efficacy of ITN in ameliorating pain among neuropathic corneal pain patients.
2. To elucidate the safety, efficacy, longevity of ITN in ameliorating pain among neuropathic corneal pain patients during a 90-day period with daily use.
3. To assess quality of life changes by treating neuropathic corneal pain with ITN during a 90-day period with daily use.

3.0 STUDY DESIGN

3.1. Study Design Description

This study is a prospective, interventional, open-label, single arm, non-randomized trial treating 45 patients with peripheral or mixed neuropathic corneal pain at their baseline exam and following 45 days and 90 days of daily use with the TrueTear™ ITN device.

3.2 Statistical analysis:

Two-tailed paired sample t-test and Pearson correlation will be performed for pain intensity, and to assess associations between different quality of life scores. Statistical comparisons of the mean values between different groups based will be performed using ANOVA.

The normality of continuous variables will be tested with the Shapiro-Wilk test. All tests will be two tailed and statistical significance will be considered for p values of less than 0.05.

4.0 SUBJECT SELECTION

4.1. Subject Inclusion Criteria:

1. Age ≥ 22 .
2. Ability to consent to study.
3. Symptoms of neuropathic corneal pain for at least 3 months, such as burning, stinging, light sensitivity, discomfort or pain.
4. Positive *in vivo* confocal microscopy (IVCM) findings for NCP such as presence of microneuromas and decreased nerve density. The presence of positive IVCM findings serves in lieu of skin biopsies as proof of nerve injury.
5. Fifty percent or more relief of pain or discomfort after instillation of Proparacaine eye drops as measured by the Visual Analogue Scale (VAS).

4.2. Subject Exclusion Criteria:

1. Clinically significant acute ocular surface diseases, such as active infectious keratitis or recent ocular surgery in the past 3 months.
2. Chronic or recurrent epistaxis, coagulation disorders.
3. Nasal or sinus surgery or significant trauma to the nose.
4. Severe nasal airway obstruction or vascularized nasal polyps.
5. Cardiac demand pacemaker, implanted or wearable defibrillator, or other implanted electronic device in the head or neck.
6. Chronic or recurrent nosebleeds
7. Bleeding disorder or another condition that can lead to increased bleeding
8. Known hypersensitivity (allergy) to the hydrogel material that contacts the nasal mucosa
9. Disabling arthritis, neuropathy, or limited motor coordination affecting self-handling of the device.
10. Allergic to benzalkonium chloride (the Co-Investigators who administer the eye drops ask all patients if they are allergic to any eye drop preservatives before proceeding with the eye drops)

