6. BIOSPECIMEN COLLECTION (IF APPLICABLE)

6.1 Specimen preparation, handling, and shipping: N/A

6.2 Instruction for specimen preparation, handling and storage: N/A

6.3 Specimen shipment: N/A

6.4 Future use of stored specimens: N/A

7. STUDY PROCEDURES

7.1 Screening/Baseline Procedures

Prospective participants, as defined by the inclusion/exclusion criteria, will be considered for entry into this study. Concurrent enrollment of subjects who are participants in other studies will be allowed based on the investigator's discretion.

During the consent process, study design and treatment regimen will be discussed with each subject. Written informed consent will be obtained before any study specific procedures are performed. However, standard of care clinical information (such as: medical history, BCVA, TBUT, staining, and Schirmer's test) obtained during a subject's clinical visit within the previous 48 hours can be used during the screening visit to determine eligibility and as their baseline assessments.

The following evaluations and procedures will be performed for all subjects during the screening period:

- Written informed consent
- Record of current ocular and systemic medications
- Record of significant medical/surgical history in the past 5 years
- Record of demographic data, including date of birth, sex, and race/ethnicity
- Eye examination (best corrected visual acuity, slit-lamp biomicroscopy, intraocular pressure)
- Corneal fluorescein staining
- Conjunctival lissamine green staining
- Tear break-up time (TBUT)
- Corneal *in vivo* confocal microscopy (IVCM)
- Ocular Surface Disease Index (OSDI) questionnaire
- Ocular Pain Assessment Survey (OPAS) questionnaire
- IDEEL QoL Questionnaire
- The following evaluations and procedures will be performed for all subjects during the Enrollment/Baseline procedures (once the patient is confirmed to be eligible): Visual Analogue Scale (VAS) questionnaire before and after each of the five tests (filter glasses response, hyperosmolar saline response, cold saline response, proparacaine challenge test) Schirmer's test II (with anesthesia)

The description of the procedures is as follows:

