Ocular Surface Disease Index (OSDI) questionnaire: (Appendix I) 12-item questionnaire designed to provide a rapid assessment of the symptoms of ocular irritation consistent with dry eye disease and their impact on vision-related functioning. The 12 items of the OSDI questionnaire are graded on a scale of 0 to 4, where 0 indicates none of the time; 1, some of the

Tufts Medical Center

time; 2, half of the time; 3, most of the time; and 4, all of the time. The total OSDI score is then calculated on the basis of the following formula: OSDI= [(sum of scores for all questions answered) x]/[(total number of questions answered) x 4].

Ocular Pain Assessment Survey (OPAS): OPAS Questionnaire (Appendix III): 27-item quantitative questionnaire designed to provide an assessment of the symptoms and quality of life effect of ocular pain. The 27 items of the OPAS questionnaire are graded on a scale of 0 to 10, or 10 to 100, where 0 indicates none and 10 or 100 indicate maximum. This questionnaire should take approximately 2-3 minutes to complete.

Visual Analogue Questionnaire: (Appendix IV) Symptoms of ocular comfort and dryness will be graded for each eye on a scale of 0-100, where 0=extremely uncomfortable, extremely dry and 100=excellent comfort, no dryness. An average rating will be provided for the morning, afternoon and evening. This questionnaire should take approximately 2-3 minutes to complete.

IDEEL QoL Questionnaire (Appendix V): This is a 27-item questionnaire, designed specifically for DED and is divided into three parts. It assesses the quality of life in three aspects of life for the previous 2 weeks: daily activities, work and feelings. The quality of life is assessed on a scale of 0-5, with zero being inability to do the activity. The score is calculated between 0 – 100 with higher scores indicating a better quality of life. This questionnaire should take about 5-10 minutes complete.

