10. STATISTICAL METHODS/DATA ANALYSIS

10.1 Primary endpoint(s) or outcome measure(s)

- Change to overall pain by the Visual Analogue Scale (VAS) after ITN stimulation

10.2 Secondary Outcome Measures:

- Change to overall pain by the Visual Analogue Scale (VAS) after daily ITN stimulation over 45-day period.
- Change to overall pain by the Visual Analogue Scale (VAS) after daily ITN stimulation over 90-day period.
- Change in quality of life as measured daily with OPAS and IDEEL
- Safety
- Tolerability
- Change in response to hypertonic solution
- Change in response to proparacaine challenge test
- Change in the intraocular pressure (IOP) measured in each visit.
- Reduction on other concomitant pain therapy

10.3 Sample Size Determination:

There is no existing systematic epidemiological study regarding the neuropathic corneal pain and there are no studies available to determine the population sample needed to detect differences between patients before and after the neuro stimulation for neuropathic corneal pain. However, based on a recent preliminary observations in 5 patients with concurrent NCP and dry eye disease, and the decrease in pain levels immediately after the use of ITN, we would achieve 80% power with an alpha error of 0.05 for pain scale intensity of 1-10, and assumption of 50% decrease in pain levels, for a sample size of 25 patients. The enrollment of 30 patients with NCP would compensate for potential dropouts.

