Appendix III: Ocular Pain Assessment Scale (OPAS) questionnaire

Ocular Pain Assessment Survey (OPAS) © 2013 Massachusetts Eye and Ear Infirmary

[figure not shown]
Please fill this form **only if** you HAVE EYE/FACIAL PAIN today or HAVE FILLED THIS FORM BEFORE

[Patient information sticker]

1. Please rate the overall severity of your pain today: (0= no pain, 10= worst pain ever)

2. On the diagram below, please shade the area where you have eye pain, and/or pain in the face and head region.

[figure not shown]

3. Do you have any longstanding pain elsewhere in your body? NO If yes, please state where: _____

[figure not shown]
ALL QUESTIONS REFER TO PAIN IN YOUR WORSE EYE. Please circle the level of your eye pain for the following:

EYE PAIN INTENSITY 24 HOURS

[figure not shown]
Level of eye pain when it is **MOST** painful:

Level of eye pain when it is **LEAST** painful:

[figure not shown]

Level of eye pain on **AVERAGE**:

[figure not shown]

EYE PAIN INTENSITY 2 WEEKS

[figure not shown]
7. in the past 2 weeks

8. in the past 2 weeks

[figure not shown]
[figure not shown]

9. in the past 2 weeks

NON-EYE PAIN

Please circle the level of your **worst non-eye pain** (pain at temples, back of head, cheek area):

Please circle the percentage of time you spend thinking about your **non-eye pain (face/head)**:

12. **Not at all** **All the time**

Tufts Medical Center

Ocular Pain Assessment Survey (OPAS) © 2013 Massachusetts Eye and Ear Infirmary

QUALITY OF LIFE (QOL)

Please circle one number that describes how much your pain has interfered with/affected the following:

Reading and/or Computer use														
13.	Not at all	0	1	2	3	4	5	6	7	8	9	10	Completely	 N/A

Driving and/or Watching TV														
14.	Not at all	0	1	2	3	4	5	6	7	8	9	10	Completely	 N/A

General activity (walking, doing house chores)														
15.	Not at all	0	1	2	3	4	5	6	7	8	9	10	Completely	 N/A

Mood														
16.	Not at all	0	1	2	3	4	5	6	7	8	9	10	Completely	 N/A

Sleep														
17.	Not at all	0	1	2	3	4	5	6	7	8	9	10	Completely	 N/A

Enjoying life/Relations with other people														
18.	Not at all	0	1	2	3	4	5	6	7	8	9	10	Completely	 N/A

Please circle the percentage of time you spend thinking about your eye pain:

19.	Not at all	0%	50%	100%	All the time
-----	------------	----	-----	------	--------------

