Appendix VII: Diary Recording (Sample Pages):
(Page 1):

[figure not shown]
(may be replicated for each ITN use)

Date:

Time:

1. Before ITN use:

[figure not shown]
Discomfort

Pain

[figure not shown]

**Photosensitivity/
Photoallodynia**

[figure not shown]
2. After ITN use:

a. Discomfort

[figure not shown]
after _____ mins of use

Pain

after _____ mins of use

**Photosensitivity/
Photoallodynia**

after _____ mins of use

3. Duration of ITN use needed: _____ minutes

4. Number of times ITN use was needed/day: _____

5. Duration of symptom-free period after ITN: _____

Tufts Medical Center

(Page 2)

(to be filled out for each day of the study)

[figure not shown]
Date:

Ocular Pain Assessment Survey (OPAS) © 2013 Massachusetts Eye and Ear Infirmary

Please fill this form **only if you HAVE EYE/FACIAL PAIN today or
HAVE FILLED THIS FORM BEFORE**

[Patient information sticker]

1. Please rate the overall severity of your pain today: (0= no pain, 10= worst pain ever)

2. On the diagram below, please shade the area where you have eye pain, and/or pain in the face and head region.

[figure not shown]
3. Do you have any longstanding pain elsewhere in your body? NO If yes, please state where:

QUALITY OF LIFE (QOL)

Please circle one number that describes how much your pain has interfered with/affected the following:

Reading and/or Computer use														
13.	Not at all	0	1	2	3	4	5	6	7	8	9	10	Completely	 N/A
Driving and/or Watching TV														
14.	Not at all	0	1	2	3	4	5	6	7	8	9	10	Completely	 N/A
General activity (walking, doing house chores)														
15.	Not at all	0	1	2	3	4	5	6	7	8	9	10	Completely	 N/A
Mood														
16.	Not at all	0	1	2	3	4	5	6	7	8	9	10	Completely	 N/A
Sleep														
17.	Not at all	0	1	2	3	4	5	6	7	8	9	10	Completely	 N/A
Enjoying life/Relations with other people														
18.	Not at all	0	1	2	3	4	5	6	7	8	9	10	Completely	 N/A

Please circle the percentage of time you spend thinking about your eye pain:

19. Not at all  All the time

AGGRAVATING FACTORS

Please circle how much your pain is increased when exposed to:

Wind, dry air, heat, air conditioning

0% 50% 100%

Severe increase

Volatile chemicals (cleaning agents, fumes, cosmetic fragrances)

0% 50% 100%

Severe increase

ASSOCIATED FACTORS

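### The printed OPAS header tells a first-time respondent without pain that day to skip the form, although the protocol schedules OPAS for every subject, so some OPAS baselines may be missing or taken only on a pain day

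*Combined protocol and SAP*

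**What the plan says.** Section 7.1 lists OPAS among the evaluations done for all subjects during screening. Section 7.2 applies the screening flowchart at the two follow-up visits, and 7.4 (Follow-up Procedures) repeats the baseline procedures at visits 2 and 3. Page 2 of the Appendix VII diary reproduces part of OPAS and is marked "to be filled out for each day of the study". Section 10.2 makes change in quality of life on OPAS and IDEEL a secondary outcome, and 10.5 names OPAS among the effectiveness questionnaires.

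The OPAS header, in Appendix III and again on diary page 2, tells the patient to complete the form only if "you HAVE EYE/FACIAL PAIN today or HAVE FILLED THIS FORM BEFORE". Item 1 of the same form has 0 for no pain.

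The entry criteria do not require pain on the day OPAS is given. Criterion 3 asks for "Symptoms of neuropathic corneal pain for at least 3 months, such as burning, stinging, light sensitivity, discomfort or pain". Criterion 5 asks that proparacaine relieve at least half of the pain or discomfort on the VAS. Neither sets a minimum score. Section 7.1 puts the proparacaine test in the enrolment block, "once the patient is confirmed to be eligible", while OPAS is in the screening block.

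**The concern.** Two instructions for the same form disagree, and the patient reads the one printed on it. Because of the filled-before clause, the restriction applies only to a patient's first form. First scores then depend on there being pain that day, and later scores do not. In a before-after comparison without a control arm, such a filter on the first reading can produce a fall with no treatment effect, and nothing in the design would separate that fall from an effect of the device. If the skipped form is simply missing, the patient has no OPAS change score, and the first-time respondents who remain are those who had pain on the screening day.

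**Working it through.** The documents give no figure for this point, so the check sets the instructions side by side and then sizes the effect under stated assumptions.

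1. **Who is told to skip.**
   - Completed OPAS before, with or without pain today: the header says complete.
   - Never completed it, eye or facial pain today: the header says complete.
   - Never completed it, no eye or facial pain today: the header says skip, while 7.1 says complete. Only this group is affected.

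2. **Whether that group can exist among enrolled patients.** Criterion 3 lists pain as one of several alternatives. Criterion 5 accepts discomfort, and 7.1 places its test outside the screening block. A patient with discomfort but no pain on the screening day can therefore meet both. The documents do not say how many such patients there would be.

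3. **What follows for that patient.**
   - (a) No baseline, so no OPAS change.
   - (b) A first form on a later pain day, with every form after it completed regardless of pain.
   - If the first form in (b) is a diary page, it may also come after device use has begun, and then it is not a pre-treatment value.

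4. **Size under (b) with no treatment effect.** Let *s* be the mean item 1 score on pain days, *f* the share of pain-free days (score 0) and *g* the share of analysed subjects affected. A first form on a pain day has expectation *s*. A later form on any day has expectation (1 − *f*)*s*. The expected change per affected patient is (1 − *f*)*s* − *s* = −*f s*, and the shift in the trial mean is −*g f s*. All values below are assumptions, with *s* = 6:

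| *f* | Fall per affected patient | Fall in mean, *g* = 10% | *g* = 20% | *g* = 40% |
|---|---|---|---|---|
| 10% | 0.6 | 0.06 | 0.12 | 0.24 |
| 20% | 1.2 | 0.12 | 0.24 | 0.48 |
| 40% | 2.4 | 0.24 | 0.48 | 0.96 |

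   The range is not a bound: patients who were pain-free at screening may have a larger *f*. The interference items follow the same algebra, with their own *s*, if they score 0 on pain-free days.

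5. **Side check on the pain endpoint.** The 25 patients in 10.3 cannot be reproduced, because neither the baseline mean nor the SD of change is given. Working backwards, 80% power at n = 25 (two-sided paired t-test, alpha 0.05) implies a standardised change *d* = 0.584. If a share *p* of patients scored zero pain before and after, *d* would become (1 − *p*)*d* / √[(1 − *p*) + *p*(1 − *p*)*d*²]. For *p* = 20% this is 0.8 × 0.584 / √(0.8 + 0.16 × 0.341) = 0.505. Power at *p* = 10%, 20% and 40%:
   - n = 25: 74%, 68%, 53%
   - n = 30 (10.3): 82%, 76%, 61%
   - n = 45 (3.1): 95%, 91%, 80%

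   With an assumed *d* of 1.0, power at n = 25 is still 98% at *p* = 20% and 88% at *p* = 40%. Every *p* here is assumed.

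**The case against.** The best defence is that the protocol text governs. If staff have everyone complete OPAS at screening, the filled-before clause is met from then on, and the conflict with the daily diary disappears. This stands as a description of the intent. It does not remove the contradiction, because the form handed to the patient still says otherwise.

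Three further points stand and limit the finding:
- Section 7.3 lists OPAS as standard of care, so some patients will have completed it already. Section 3.1 also describes a "non-randomized trial treating 45 patients with peripheral or mixed neuropathic corneal pain", so patients free of pain on the screening day may be few.
- No rule makes a later pain-day form the baseline. The bias towards improvement is therefore conditional, and the alternative is a missing baseline.
- OPAS serves a secondary outcome.

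A reader might go further and infer that criterion 3 admits patients with light sensitivity alone, who cannot contribute to the primary endpoint, "Change to overall pain by the Visual Analogue Scale (VAS) after ITN stimulation". The documents do not support that. The criteria apply together, and a patient with neither pain nor discomfort at the proparacaine test has nothing to relieve and fails criterion 5. VAS is scheduled for every subject, and 7.1 describes it thus: "Symptoms of ocular comfort and dryness will be graded for each eye on a scale of 0-100, where 0=extremely uncomfortable, extremely dry". On that scale a patient with discomfort alone has a score with room to improve. The Appendix IV form does not appear in the text reviewed, so its item wording could not be checked.

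**Conclusion.** The point holds as a narrow inconsistency between the OPAS header and 7.1, 7.2, 7.4 (Follow-up Procedures) and the diary marking. It affects first-time respondents without eye or facial pain on the day, in an unknown number. The consequence is a missing OPAS baseline or, if a later pain-day form is used instead, a comparison that favours apparent improvement. The 0.06 to 0.96 points shown rest entirely on assumed values of *s*, *f* and *g*.

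A reader might also infer that a minimum pain score at entry is needed to protect power. That does not follow. The loss depends on an unknown share of zero-pain patients and an unstated SD. Section 2.0 cites relief of pain or photoallodynia as the motivating observation, so admitting a wider symptom range is a defensible choice in a pilot. What remains is a secondary comment: criteria 3 and 5 set no minimum pain score and accept discomfort without pain, so some patients may have little room to improve on a true pain score.

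**What to change.** On the study copies of OPAS in Appendices III and VII, delete the only-if instruction, or override it in 7.1 and 7.4 (Follow-up Procedures). State that every subject completes OPAS at screening, at each visit and on each diary day, scoring 0 for no pain, and that the OPAS taken before any ITN use is the baseline. Because the interference items offer an N/A box, say that absence of pain is scored 0 and not N/A.

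The cost is one line and a minor departure from the printed header of a copyrighted form. Overriding it in the protocol leaves the form itself unchanged.

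As a comment and not a required change, the sponsor should reconcile criteria 3 and 5, the timing of the proparacaine test in 7.1, the overall-pain endpoint in 10.1 and the comfort and dryness VAS described in 7.1.
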